11.4 Exploratory Objectives Analysis

Exploratory immunogenicity endpoints are:

1. Predominant isotype of the RSV-specific serum antibody at multiple time points.
2. RSV-specific immune response against different RSV group A and group B strains or engineered RSV antigens at multiple time points.
3. Frequency of B cells secreting RSV-specific antibodies at Day 1 (baseline), Day 8 (seven days after the first dose), Day 29 (28 days after the first dose), and Day 181 (six months after the first dose).
4. Diversity of the B-cell repertoire at Day 1 (baseline), Day 8 (seven days after the first dose), Day 29 (28 days after the first dose), and Day 181 (six months after the first dose).

The frequency of B cells secreting RSV-specific antibodies will be determined by ELISPOT at Day 1 (baseline), Day 8 (seven days after the first dose), Day 29 (28 days after the first dose), and Day 181 (six months after the first dose) in order to evaluate the baseline specific B-cell frequency (Day 1 baseline), the peak of plasmablast responses (Day 8), the peak of B cell memory responses (Day 29), and the persistence of memory B cell responses (Day 181).

Analysis Method:

The percentage of subjects with detectable frequencies of IgG+ and IgM+ RSV-MBC and HSA-MBC will be summarized using two-sided 95% Clopper-Pearson CIs by each treatment group within each cohort at days 1, 8, 29 and 181.

The number of circulating IgG+ and IgM+ RSV-specific plasmablasts (expressed as ASC/million PBMC) at Day 8 and the frequencies of circulating IgG+ and IgM+ RSV-

MBC and HSA-MBC (expressed as percentage of antigen-specific MBC/Total IgG and antigen-specific MBC/Total IgM) at Days 1, 29 and 181 will be summarized using medians and corresponding two-sided, 95% CIs around the median by each treatment group within each cohort. Summary statistics will be completed by providing minimum, maximum, first and third quartiles as well as the mean. To test for differences between treatment groups, the Kruskal-Wallis test will be performed. Pairwise testing of the treatment groups will be performed using the Hodges-Lehmann approach which provides the median of the pairwise difference of the dose groups along with its 95% CI.

When baseline day 1 values are non-zero, the fold changes of circulating MBC from Day 1 to Day 29 and to Day 181; and, the fold change from Day 29 to 181 will be summarized using medians and corresponding two-sided, 95% CIs around the median by each treatment group within each cohort. Summary statistics will be completed by providing minimum, maximum, first and third quartiles as well as the mean.

The median number of IgG+ and IgM+ plasmablasts per million PBMC (y-axis) will be plotted against treatment group (x-axis) differentiating each dosage and adjuvant group by symbol or color. Similarly, the median frequencies of IgG+ and IgM+ RSV-specific MBC (y-axis) at Day 1, Day 29 and Day 181 will be plotted against treatment group (x-axis) differentiating each dosage and adjuvant group by symbol or color.

Other exploratory endpoints may be analyzed at a later time point and included in a separate addendum to the CSR.

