Assess for AESIs ^p		X		X		X		X		X	X	X	X	X	X
Prior/Concomitant Medications/vaccines ^q	X	X		X		X		X		X	X	X	X	X	
Study Termination ^r															X

- Physical examination must be performed by a qualified health professional in accordance with local regulations and licensing requirements designated within the Site Responsibility Delegation Log. See protocol [section 6.2](#) for components of physical examination by visit.
- Procedure to be performed prior to vaccination.
- Safety laboratory assays that will be included are listed in protocol [section 3.5.3](#).
- Urinalysis testing will include at a minimum protein, glucose, and presence of red blood cells.

- e. Maximal blood draw refers to volume drawn for each type of assay at each specified visit. See protocol [section 3.5.1](#) for greater detail regarding blood sampling volumes.
- f. The first 10 subjects enrolled in each treatment group of Cohort 3 who agree to the additional blood draws will need to sign an additional consent prior to the blood draw for the secondary exploratory objective.
- g. Subjects will receive two doses of vaccine or placebo according to the study randomization scheme.
- h. A 30 minute post-injection local and systemic adverse event and body temperature measurement will be performed by the subject under site staff supervision at the clinic during Visit 1 and Visit 5.
- i. Beginning 6 hours following study vaccine administration at Visit 1 and Visit 5, and daily thereafter through 7 days after each vaccination, solicited local and systemic adverse events including other reactions (i.e. body temperature measurements and use of analgesics/antipyretics) will be reported daily by the subject on a diary card.
- j. Subjects will receive training on the diary card at Visit 1 and Visit 5.
- k. The diary card will be dispensed at Visit 1 and Visit 5, and subjects will be reminded that diary cards must be returned at the next clinic visit (Visit 2 or Visit 6).
- l. Site staff will contact subjects by phone 2 and 4 days after each vaccination to remind them to complete their diary cards each day, and to bring the diary cards to their next clinic visit.
- m. Review of safety data captured on diary cards will be completed at Visit 2 and Visit 6. Diary cards will be collected and stored with subject files.

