4. RANDOMIZATION AND BLINDING

4.1 Method of Group Assignment and Randomization

Subjects will be enrolled in a stepwise dosage-escalation manner into one of three cohorts:

- Cohort 1: low dosage of RSV F subunit vaccine [45 µg],
- Cohort 2: middle dosage of RSV F subunit vaccine [90 µg], and
- Cohort 3: high dosage of RSV F subunit vaccine [135 µg]).

Within each cohort, subjects will be randomly allocated (1:1:1:1) to receive vaccine with no adjuvant, vaccine with aluminum hydroxide, vaccine with MF59, or placebo, as outlined in [Table 4.1](#). All subjects will receive two doses of a 0.5 mL intramuscular injection of the vaccine with adjuvant (aluminum hydroxide [1 mg] or MF59 [0.25 mL; 9.75 mg squalene and surfactants]), the vaccine without adjuvant, or saline placebo. There will be approximately 24 subjects in each active treatment group, and 24 placebo subjects in each cohort.

Table 4.1.

Cohort	Dosage	Route of Administration	Regimen: Two Doses †		
			No Adjuvant	Al(OH) ₃ ‡	MF59 ‡
1	45 µg	IM (0.5 mL)	24	24	24
	Placebo (saline)	IM (0.5 mL)	24		
2	90 µg	IM (0.5 mL)	24	24	24
	Placebo (saline)	IM (0.5 mL)	24		
3	135 µg	IM (0.5 mL)	24	24	24
	Placebo (saline)	IM (0.5 mL)	24		

For further details please refer to [section 5.1. of the protocol](#).

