7.5 Exploratory (EXP) Immunogenicity Set

All subjects included in Cohort 3 who signed an additional exploratory objective informed consent form who:

- Correctly receive the vaccine (i.e., receive the vaccine to which the subject is randomized and at the scheduled time points).
- Have no major protocol deviations leading to exclusion (see [section 6.2](#)) as defined prior to unblinding / analysis.
- Are not excluded due to other reasons defined prior to unblinding or analysis (see [section 6.2](#))

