8. GENERAL ISSUES FOR STATISTICAL ANALYSES

8.1 Adjustment for Covariates

The log-transformed antibody titers at the time points where a blood draw for immunogenicity is collected will be analyzed using an Analysis of Covariance (ANCOVA) model which includes the vaccine-group effect (see [section 11.2](#)) and an effect defined by the log-transformed pre-vaccination antibody titer as an independent variable. Summary tables will show adjusted geometric mean titers (GMTs) for each vaccine group.

Binary data tables will show unadjusted percentages.

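### Memory B-cell frequencies are compared between arms of about 10 without using the Day 1 frequency measured in the same subjects: a valid analysis that gives up precision

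*SAP*

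**What the plan says.** All references are to the last of the three SAP versions in the file; the two before it left the exploratory analysis to a separate plan.

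- **Who is analysed.** The B-cell subset is "The first 10 subjects enrolled in each treatment group of Cohort 3 who agree to the additional blood draws" (Section 3, Table 3-1, footnote f). The analysis set in Section 7.5 is "All subjects included in Cohort 3 who signed an additional exploratory objective informed consent form who" were correctly vaccinated and had no excluding deviation. Section 4.1 gives four arms: "Within each cohort, subjects will be randomly allocated (1:1:1:1) to receive vaccine with no adjuvant, vaccine with aluminum hydroxide, vaccine with MF59, or placebo". That makes about 40 subjects, fewer after exclusions.
- **What is analysed.** In Section 11.4 the outcome is the frequency itself at each day: "MBC and HSA-MBC (expressed as percentage of antigen-specific MBC/Total IgG and antigen-specific MBC/Total IgM) at Days 1, 29 and 181 will be summarized".
- **How arms are compared.** "To test for differences between treatment groups, the Kruskal-Wallis test will be performed". Then: "Pairwise testing of the treatment groups will be performed using the Hodges-Lehmann approach which provides the median of the pairwise difference". No covariate is named for either, and neither sentence says which days it covers.
- **Where Day 1 appears.** Section 11.4 uses Day 1 in the detectable percentages, the per-arm medians and the plots. It also gives per-arm median fold changes with 95% CIs, limited to subjects whose Day 1 value is not zero. No between-arm comparison of those fold changes is named.
- **Serum titers, for contrast.** Section 8.1 puts into the ANCOVA "an effect defined by the log-transformed pre-vaccination antibody titer as an independent variable". Section 11.2 repeats this in its models, and Section 11.3 uses the Day 1 neutralizing titer as covariate for the ratio analyses.

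**The concern.** Adults enter this study with RSV immunity: Section 1 says nearly all children have been infected by two to three years of age. A Day 29 or Day 181 MBC frequency therefore contains what the subject brought to the trial as well as what the vaccine added. If subjects differ at Day 1 and the difference persists, it goes into the error of the Kruskal-Wallis test and the Hodges-Lehmann intervals.

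The Day 1 value that would remove part of this noise is already collected in the same subjects. The SAP uses this kind of adjustment in its titer models, where groups have about 24 subjects, but not here, where arms have about 10. At stake is the chance of seeing an adjuvant effect on B-cell memory, and the width of the intervals around it.

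**Working it through.** **Inputs from the SAP.** 10 per arm and 4 arms (Section 3 footnote f; Section 4.1). The SAP gives no power, effect size, SD, Day 1 to post-dose correlation or significance level for this subset, so there is no stated figure to reproduce.

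**Assumptions.** Two-sided 0.05; effects in SD units of the raw log frequency; equal variances at Day 1 and post-dose; correlation ρ between them from 0 to 0.8.

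**Step 1: pairwise, normal approximation.** Adjusting for Day 1 leaves residual SD s = √(1 − ρ²), so the share of variance removed is ρ². With n = 10 per arm:

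- power for a 1 SD difference = Φ(√(n/2)/s − 1.96) = Φ(2.236/s − 1.96)
- difference detectable with 80% power = (1.96 + 0.842) × s × √(2/10) = 1.253 × s
- n per arm for 80% power at 1 SD = 2 × (1.96 + 0.842)² × s² = 15.7 × s², rounded up

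| ρ | variance removed | s | power at 1 SD | detectable difference | n per arm |
|---|---|---|---|---|---|
| 0 (same as unadjusted) | 0% | 1.000 | 0.61 | 1.25 SD | 16 |
| 0.3 | 9% | 0.954 | 0.65 | 1.20 SD | 15 |
| 0.5 | 25% | 0.866 | 0.73 | 1.09 SD | 12 |
| 0.7 | 49% | 0.714 | 0.88 | 0.90 SD | 9 |
| 0.8 | 64% | 0.600 | 0.96 | 0.75 SD | 6 |

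**Step 2: global test, simulation.** Four arms of 10, normal data, 4,000 runs per case. Kruskal-Wallis on raw values is set against Quade: rank the post-dose and Day 1 values, regress one set of ranks on the other, and run a one-way ANOVA on the residuals.

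| ρ | three arms +1.2 SD: Kruskal-Wallis | Quade | one arm +1 SD: Kruskal-Wallis | Quade |
|---|---|---|---|---|
| 0 | 0.71 | 0.72 | 0.53 | 0.54 |
| 0.3 | 0.70 | 0.74 | 0.51 | 0.57 |
| 0.5 | 0.70 | 0.81 | 0.53 | 0.66 |
| 0.7 | 0.70 | 0.93 | 0.53 | 0.81 |

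Repeat runs of the 1.2 SD case gave 0.68 to 0.70 for Kruskal-Wallis and 0.73, 0.82 to 0.83 and 0.93 for Quade at ρ = 0.3, 0.5 and 0.7.

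**Step 3: type I error.** Null rejection was 0.037 to 0.049 for Kruskal-Wallis. For Quade it was 0.043 to 0.057, apart from one case at 0.064. Kruskal-Wallis runs slightly under 5%, so about one point of each gain in Step 2 is calibration; the 0.01 difference at ρ = 0 is of that size.

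**Step 4: zeros at Day 1.** With half of the Day 1 values tied at a floor, Quade gave 0.73, 0.80 and 0.90 at ρ = 0.3, 0.5 and 0.7 (three arms +1.2 SD). Most of the gain survives and no subject is dropped.

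**Step 5: is change from Day 1 an alternative?** With equal variances, a change score has variance 2(1 − ρ) against 1 for the raw value: 1.4 at ρ = 0.3, 1.0 at 0.5 and 0.6 at 0.7. It is less precise than the raw value whenever ρ < 0.5. Wilcoxon tests of 10 against 10 at 1.2 SD, raw against change, gave 0.68 and 0.53 at ρ = 0.3, 0.66 and 0.67 at 0.5, and 0.66 and 0.88 at 0.7.

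**The case against.** The case for leaving the plan alone has weight. Post-dose levels compared between randomised arms estimate a vaccine effect, and Kruskal-Wallis holds its level. Section 8.4 says tests are descriptive only, the subset is about 40 subjects in a Phase 1 study, and no decision or power target hangs on it. The gain depends on a correlation nobody has stated; at 0.3 it is about 4 points (0.70 to 0.74). All of this stands, and it limits the point to efficiency.

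A reader might infer more than the document supports:

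- **That chance differences in Day 1 memory make the test unreliable or produce false adjuvant effects.** They do not beyond the nominal rate: arms are randomised within the cohort, and null rejection was at or below 5%.
- **That every serum analysis in the SAP adjusts for baseline.** Only the ANCOVA comparisons do. Unadjusted GMTs (Section 11.2), binary tables (Section 8.1), and third-quartile proportions and reverse cumulative distributions (Section 11.3) do not.
- **That Section 11.4 ignores Day 1.** It reports Day 1 in several per-arm summaries, including fold changes with CIs. What is missing is its use in a comparison between arms.
- **That a Day 1 test is expressly planned.** The Kruskal-Wallis sentence follows a list that includes Day 1 but names no days. A Day 1 display also serves the stated objective of exploring baseline immunity.
- **That comparing changes from Day 1 is the remedy.** Step 5 shows that it can make matters worse.

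**Conclusion.** The point holds as a loss of precision, not as bias or invalidity. The between-arm MBC test and the pairwise differences leave out a covariate that is already measured, in the analysis with the smallest arms in the SAP. For three vaccine arms shifted by 1.2 SD, adjusted global power is about 0.73, 0.82 and 0.93 against about 0.70, at correlations of 0.3, 0.5 and 0.7, and nothing is lost at zero correlation.

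These figures rest on assumed shifts and correlations, normal data and a full 10 per arm. The gain is small if Day 1 predicts later frequency weakly and substantial if the correlation is 0.7 or more. The Day 8 plasmablast comparison is not affected, as plasmablasts are summarised at Day 8 only. Because the endpoint is exploratory and the tests descriptive, the change is optional to modest in priority.

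**What to change.** In Section 11.4, for MBC frequencies at Days 29 and 181:

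- Replace the unadjusted Kruskal-Wallis test with a Quade rank analysis of covariance, using the Day 1 frequency of the same analyte as covariate (IgG+ with IgG+, IgM+ with IgM+). Ranks accept zero Day 1 values.
- Base the pairwise tests on the residuals from that same analysis, so that the global and pairwise results address the same quantity.
- Keep the raw medians, raw-scale Hodges-Lehmann estimates with CIs and fold changes, labelled as description. State that the raw intervals are unadjusted and may not match the adjusted p-values.
- Do not use change-from-Day-1 scores for the pairwise comparison.
- State that Day 1 is shown descriptively only, and leave the Day 8 plasmablast test as it is.

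The cost is a few lines of SAP text and code; no new data are needed. The change should be written in before the B-cell data are unblinded.

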12. EFFICACY ANALYSIS

12.1 Primary Objectives Analysis

Not Applicable.

12.2 Secondary Objectives Analysis

Not Applicable.

12.3 Exploratory Objectives Analysis

Not Applicable.

13. SAFETY ANALYSIS

The analysis of safety assessments in this study will include summaries of the following categories of safety data collected for each subject:

- Vaccine exposure.
- Solicited local and systemic adverse events and indicators of solicited adverse events.
- Unsolicited adverse events.
- Clinical Laboratory Investigations.

13.1 Analysis of Extent of Exposure

The frequencies and percentages of subjects with vaccinations will be summarized overall and by vaccine group. Data will be tabulated for the All Enrolled Set.

13.1.1 Safety Completeness Analysis

Solicited adverse events

The safety completeness analysis on solicited adverse events aims to identify subjects who completed diary cards, irrespective of severity. The analysis will show the number of subjects with *valid data* by solicited adverse event and time point. *Valid data* in the context of the safety completeness analysis are all data entered in the diary card (including implausible values) except “Not done/unknown”.

Four summaries will be produced:

1. The frequencies of subjects who provide diary cards by vaccine group and collection method (i.e., clinical visit, postal mail).
2. For each solicited adverse event, the frequencies of subjects with *valid data* will be presented by vaccine group and time point: 30 min, 6h, days 2, 3, 4, 5, 6 and 7
3. For each type of solicited adverse event (local, systemic) and indicators of solicited adverse events, such as analgesic use, the frequencies of subjects *with valid data* by vaccine group, aggregated over time points: 6h - day 7
4. For each solicited adverse event, the frequencies of subjects *with valid data* by vaccine group, aggregated over time points: 6h - day 7

For the corresponding percentages, the denominator will be the respective numbers of exposed subjects, i.e., subjects who received a vaccination and were still in-study for that time point or time interval, irrespective of whether a diary card was present or not.

All analyses will be based on the ‘as treated’ analysis set.

13.2 Solicited Local and Systemic Adverse Events

For details please refer to [section 7.1.1 of the protocol](#).

Only solicited local and systemic adverse events reported in the diary card will be analyzed. Implausible measurements will not be taken into consideration in the analysis but listed in the Appendix.

Solicited adverse events will be reported at 30 minutes, at approximately 6 hours post-vaccination on day 1 and then daily until day 7 using structured diaries. The analyses of solicited adverse events will be done separately for 30 minutes and based on three intervals: 6h - day 3, day 4 - 7 and 6h - day 7, each without 30 minutes data. In addition solicited adverse events ongoing after day 7 will be presented as unsolicited AEs.

For erythema, induration and swelling recorded originally as diameters (mm), the following categorization will be used to summarize the data:

Grade 0 (< 25 mm), any (25-50 mm, 51-100 mm, >100 mm)

Body temperature will be broken down by route of measurement according to the recommendations of the Brighton collaboration and will be summarized according to the 3 schemes described below:

- by 0.5 °C increments: <36.0, ≥36.0-<36.5, ≥36.5-<37.0, ≥37.0-<37.5, ≥37.5-<38.0, ≥38.0-<38.5, ≥38.5-<39.0, ≥39.0-<39.5, ≥39.5-<40.0, ≥40.0°C
- by 1.0 °C increments: <36.0, ≥36.0-<37.0, ≥37.0-<38.0, ≥ 38.0-<39.0, ≥39.0-<40, ≥40°C
- <38.0, ≥38.0 °C

Fever, defined as a body temperature of ≥38°C irrespective of route of measurement, will be integrated to the summaries as an indicator of a systemic adverse event.

The analyses will encompass summaries of the data on five levels:

1. Daily reports of subjects with solicited adverse events.
2. Time of first onset of solicited adverse events (excluding 30 min measurement).
3. Solicited adverse events, maximum event severity by event and interval (6h - day 3, day 4 -7, and 6h - day 7, each without 30 min).
4. Duration of solicited adverse events.
5. Solicited adverse events and indicators of solicited adverse events, occurrence of at least one event by category (local, systemic) and interval (6h-Day 3, Day 4-7 and 6h-Day 7, each without 30 min).

For each of the time points or time intervals presented in the summaries, only subjects with at least one plausible observation (i.e., any non-missing values but excluding “Not done/unknown” and implausible values) for the solicited adverse events in the interval of interest will be considered. Subjects without plausible data (i.e. missing values or reported as “Not done/unknown” and implausible values) will be removed from the denominator to prevent a downward bias (towards zero).

Level 1: Daily reports of solicited adverse event

For each of the time points only subjects with at least one plausible observation (i.e., any non-missing values but excluding “Not done/unknown” and implausible values) for the solicited adverse event in the interval of interest will be considered. Subjects without plausible data (i.e. missing values or reported as “Not done/unknown” and implausible values) will be removed from the denominator in order to prevent a downward bias (towards zero). Data collected will be summarized (frequencies and percentages of subjects) by vaccine group, solicited adverse event, vaccination number and time point.

Level 2: Time of first onset of solicited adverse events

The **time of first onset** is defined, for each subject, for each solicited adverse event, as the time point at which the respective solicited adverse event first occurred. For erythema, induration and swelling the following threshold will be used ≥ 25 mm. The summary will provide the frequencies and percentages of subjects with first onset of each solicited adverse events by vaccine group, by vaccination number, and by each time point.

The tables below show examples of a listing considering four subjects who receive two vaccinations, with post-vaccination data for a given solicited adverse event and a summary table by vaccination group.

Table 13.2-1: Example for Time to First Onset of Solicited Adverse Events

Vaccination	Subject Number	6 Hours	Day 2	Day 3	Day 4	...	Day 7
1	PP D	None	Severe	Moderate	None	...	None
	PP D	Mild	None	None	Moderate	...	Missing
	PP D	Moderate	Mild	None	Severe	...	Mild
	PP D	Mild	Mild	None	None	...	None
2	PP D	None	None	None	None	...	Not done
	PP D	None	Mild	Mild	Missing	...	Missing
	PP D	Severe	None	Mild	Missing	...	None
	PP D	Missing	Missing	Missing	Severe	...	Mild

For each vaccination the first onset of the adverse event will be used for each subject. For any vaccination the worst adverse event across all vaccinations per time point will be used. Note, ‘not done’ is treated identical to ‘missing’.

Table 13.2-2: Time to First Onset of Solicited Adverse Events

Vaccine group A

Vaccination	Adverse event	Number (%) of Subjects						...	DAY 7 (N=4)
		6 HRS (N=4)	DAY 2 (N=4)	DAY 3 (N=4)	DAY 4 (N=4)				
1	XY	n	4	4	4	4	...	3	
		ANY	3 (75.0%)	1 (25.0%)	0 (0%)	0 (0%)	...	0 (0%)	
		Mild	2 (50.0%)	0 (0%)	0 (0%)	0 (0%)	...	0 (0%)	
		Moderate	1 (25.0%)	0 (0%)	0 (0%)	0 (0%)	...	0 (0%)	
		Severe	0 (0%)	1 (25.0%)	0 (0%)	0 (0%)	...	0 (0%)	
2	XY	n	3	3	3	2	...	2	
		ANY	1 (33.3%)	1 (33.3%)	0 (0%)	1 (50.0%)	...	0 (0%)	
		Mild	0 (0%)	1 (33.3%)	0 (0%)	0 (0%)	...	0 (0%)	
		Moderate	0 (0%)	0 (0%)	0 (0%)	0 (0%)	...	0 (0%)	
		Severe	1 (33.3%)	0 (0%)	0 (0%)	1 (50.0%)	...	0 (0%)	
ANY	XY	n	4	4	4	4	...	3	
		ANY	3 (75.0%)	1 (25.0%)	0 (0%)	0 (0%)	...	0 (0%)	
		Mild	2 (50.0%)	0 (0%)	0 (0%)	0 (0%)	...	0 (0%)	
		Moderate	0 (0%)	0 (0%)	0 (0%)	0 (0%)	...	0 (0%)	
		Severe	1 (25.0%)	1 (25.0%)	0 (0%)	0 (0%)	...	0 (0%)	

N: no. of subjects with data at a time point across all vaccinations.

n: no. of subjects with data at a time point for that specific vaccination.

Level 3: Solicited adverse events, maximum event severity by event and interval

The **maximum event severity** will be defined if there is at least one plausible non-missing observation (excluding “Not done/unknown” and implausible values) within this time interval. Each subject’s data will be aggregated across the time points of the interval and summarized according to the maximal severity observed for each adverse event, followed by a summary across subjects for each vaccine. Subjects without any solicited adverse events in the interval, i.e., missing values at each of the requested time points,

will be removed from the denominator. Data collected will be summarized (frequencies and percentages of subjects) by vaccine group, solicited adverse event, vaccination number and time point.

Level 4: Number of days with solicited adverse events

The number of days with the adverse event is defined irrespective of severity. This means at least ‘mild’ solicited adverse event that are assessed qualitatively and ≥ 25 mm for erythema, induration and swelling. If a solicited adverse event continues beyond day 7 the period after day 7 is added.

The following example is used to illustrate how the duration is calculated:

Suppose six subjects, who received a vaccination have the post-vaccination solicited adverse event data shown in the table below. In addition, there are unsolicited adverse event reports indicating that the adverse event in subject ^{PPD} and ^{PPD} continued until day 12 and day 8, respectively. For subject ^{PPD} the number of days is calculated as 6+5 and for subject ^{PPD} as 3+1. Missing values (‘Missing’) are not taken into consideration

Table 13.2-3: Example for Number of Days With Solicited Adverse Events

Subject Number	6 Hours	Day 2	Day 3	Day 4	Day 5	Day 6	Day 7	No. of days
^{PPD}	None	Severe	Moderate	None	None	None	None	2
^{PPD}	Mild	None	None	Moderate	Moderate	Moderate	Missing	4
^{PPD}	Moderate	Mild	None	Severe	Severe	Severe	Mild ^a	11
^{PPD}	None	None	None	None	None	None	Not done	0
^{PPD}	None	Mild	Mild	Missing	Missing	Missing	Missing	2
^{PPD}	Severe	None	Mild	None	None	None	Severe ^b	4

^a continued until day 12; ^b continued until day 8

The frequency distribution of the number of days will be provided in a summary table by vaccine group, vaccination number, and by solicited adverse event.

Level 5: Solicited adverse events, occurrence of at least one event by category (local, systemic) and interval.

The **occurrence of at least one solicited adverse event** is defined as “any” for a subject if he/she reports greater than “none” ≥ 25 mm, for erythema, swelling, and induration) for the respective event and “none” otherwise. The occurrence of at least one solicited adverse event (i.e., none versus any) will be summarized by category (i.e., local, systemic,

any), by vaccine group, by vaccination (after each vaccination and after any vaccination) and by time interval.

Medications to treat or prevent pain or fever will be summarized by frequencies and percentages of subjects reporting use of the medications by interval (30 min, 6h - day 3, day 4 - 7, 6h - day 7).

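### SAP Table 13.2-2 (time of first onset) divides once-only onsets by a day-by-day denominator, separately dates an onset after missing entries as if it were known, and has a wrong Day 7 N

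*SAP*

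**What the plan says.** The point concerns Level 2 in SAP section 13.2. The file holds three successive versions of the SAP, and the rule and tables are the same in all of them.

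- **Definition.** Time of first onset is defined, per subject and per reaction, "as the time point at which the respective solicited adverse event first occurred".
- **Counting.** "For each vaccination the first onset of the adverse event will be used for each subject".
- **Output.** "The summary will provide the frequencies and percentages of subjects with first onset of each solicited adverse events", by vaccine group, vaccination number and time point.
- **General denominator rule, for all levels.** Subjects without plausible data at a time point or interval "will be removed from the denominator to prevent a downward bias (towards zero").
- **Footnotes to Table 13.2-2.** "n: no. of subjects with data at a time point for that specific vaccination" and "N: no. of subjects with data at a time point across all vaccinations".
- **Missing entries.** An entry of not done "is treated identical to" missing. Section 8.2.1 adds that missing safety values are not imputed.

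Table 13.2-1 gives an example with "four subjects who receive two vaccinations", and Table 13.2-2 shows the summary derived from it. There is no category for a reaction whose onset time cannot be determined.

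**The concern.** First onset places a subject in at most one column per vaccination. Percentages across the columns should therefore add up to the share of subjects who had the reaction, and they cannot sensibly exceed 100%. A denominator that moves with each day's diary gaps breaks that property.

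A second question is separate from the denominator: what to do when the first positive entry follows missing ones. The onset then lies somewhere in the gap, but the table gives it a definite day.

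Onset timing is one of five planned summaries of solicited reactions, and safety compared with placebo is a primary objective. The worked example also shows programmers how to derive the table. A second programmer checking the safety programs under section 16 against this example would confirm the rule, not question it.

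**Working it through.** **Inputs.** Vaccination 2 entries from Table 13.2-1, in row order (Days 5 and 6 are not displayed; not done is shown as missing):

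| Subject | 6 h | Day 2 | Day 3 | Day 4 | Day 7 | First positive entry |
|---|---|---|---|---|---|---|
| 1 | None | None | None | None | missing | none displayed |
| 2 | None | Mild | Mild | missing | missing | Day 2, mild |
| 3 | Severe | None | Mild | missing | None | 6 h, severe |
| 4 | missing | missing | missing | Severe | Mild | Day 4, severe |

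**Step 1: reproduce the plan's figures.** Percentage = first onsets at the time point / subjects with an entry at that time point.

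| | 6 h | Day 2 | Day 3 | Day 4 | Day 7 |
|---|---|---|---|---|---|
| First onsets | 1 | 1 | 0 | 1 | 0 |
| n | 3 | 3 | 3 | 2 | 2 |
| Percentage | 33.3 | 33.3 | 0 | 50.0 | 0 |

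This is exactly the n row and the ANY row that the SAP prints for Vaccination 2. The same recount reproduces these rows for Vaccination 1 and for the any-vaccination block.

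**Step 2: add across the displayed columns.**
- Any severity: 1/3 + 1/3 + 0 + 1/2 + 0 = 116.7%. Subjects reacting in the displayed columns: 3/4 = 75%.
- Severe: 1/3 + 1/2 = 83.3%. Subjects whose first onset is tabulated as severe: 2/4 = 50%.
- Vaccination 1 and the any-vaccination block each total 75.0 + 25.0 = 100%, because n is 4 in every column that contains an onset.

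**Step 3: is it an at-risk rate instead?** Such a rate would divide by subjects with an entry and no earlier onset: 3, 2, 1, 2, 0. The percentages would be 33.3, 50.0, 0 and 50.0, with nobody at risk on Day 7. The SAP prints n = 3, 3, 3, 2, 2. Subject 3 stays in n on Days 2 and 3 and subject 2 on Day 3, after their onsets. Both then leave n on Day 4 only because the diary is blank.

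**Step 4: fixed denominator.** All four subjects have at least one entry after Vaccination 2, so each column is divided by 4: 25%, 25%, 0%, 25%, 0%, total 75%.

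**Step 5: the unknown onset.** Subject 4 has no entry at 6 h, Day 2 or Day 3. The onset could lie anywhere from 6 h to Day 4, but Table 13.2-2 prints it as a severe first onset on Day 4. Step 4 does not cure this: the subject still sits under Day 4, at 25%. With an unknown-onset column the row becomes 25%, 25%, 0%, 0%, 0% and 25% unknown (by Day 4), again totalling 75%.

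**Step 6: Day 7 N.** The second subject has no Day 7 entry after either vaccination; the other three have one after at least one vaccination. By its footnote N is 3. The header prints 4, while the any-vaccination block of the same table prints n = 3.

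**Step 7: size at about 24 per group.** One onset is 1/24 = 4.2% with complete entries, 1/22 = 4.5% with two missing that day, and 1/19 = 5.3% with five missing.

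**The case against.** The printed percentages are not miscalculated: they follow from a rule that the SAP states openly, with a reason, and n is printed above every column. The SAP never says that the columns add up to anything, and a reader can recalculate from the counts. The example is artificial: 7 of the 20 displayed Vaccination 2 entries are missing. Incidence and maximum severity come from Levels 3 and 5 over whole intervals, and diary completeness is reported separately under section 13.1.1. A fixed denominator also treats a subject with no 6 h entry as having no 6 h onset, which is the downward bias the SAP wants to avoid.

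Much of this stands. It limits the size of the point and means that the fault lies in the rule, not in the division. The bias argument also has force at 6 h, where subject 4's status really is unknown. It fails on Day 4. Subjects 2 and 3 had already had their onset, so they are known not to be Day 4 first onsets whatever the diary shows. Removing them prevents no bias and doubles the figure from 25% to 50%. The rationale suits the daily reports of Level 1, not a once-only classification.

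A reader might infer that the changing denominator creates the false Day 4 onset. It does not; the two defects are independent. Nor do missing later entries always inflate the table. In Vaccination 1 n falls to 3 on Day 7 and the row still totals 100%, because no onset is counted there. The effect is not confined to late columns either: in Vaccination 2 the 6 h and Day 2 figures also rise, from 25% to 33.3%.

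**Conclusion.** The point holds: two separate defects and one slip in Table 13.2-2.

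1. The per-time-point denominator gives percentages that cannot be read as onset timing. In the Vaccination 2 example they total 116.7% against 75%, and 83.3% against 50% for severe.
2. Independently, an onset after missing entries is dated to the first recorded positive day.
3. The Day 7 header N should be 3.

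The 75% and 50% refer to the displayed columns only, since Days 5 and 6 are not shown and subject 1 could have reacted then. Any further onset on those days could only add to the 116.7%.

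The denominator defect changes only columns in which an onset is counted while some subjects have no entry. The dating defect arises only where the first positive entry follows missing ones. The 117% comes from a toy example and does not predict the error in the trial: at about 24 per group one onset moves from 4.2% to 5.3% if five entries are missing. How often that happens depends on diary completion, for which the SAP gives no figure.

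The documents do not support reading this as a flaw in the safety conclusions at large. The severe reaction was really recorded on Day 4, and only its onset is uncertain. Apart from the day assigned to such onsets, the counts are right, and Levels 3 and 5 are unaffected. The table should be corrected before programming, but it is one descriptive table.

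**What to change.** - For each vaccination block and for the any-vaccination block, use one fixed denominator for all first-onset columns: subjects with at least one plausible entry for that reaction from 6 h to Day 7. State in section 13.2 that Level 2 departs from the general denominator rule, and why.
- Where the entry immediately before the first positive one is missing, not done or implausible, tabulate the subject under an added column for onset time unknown (by Day x). This includes every subject whose first positive entry is later than 6 h and has no plausible entry before it. An earlier gap followed by a recorded None is then treated as no onset; the SAP should say so.
- Correct Table 13.2-2, including the Day 7 N, which becomes 3 if that header is kept with its present footnote.

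The cost is revised wording, one corrected example, slightly more programming and one extra column. No new data are needed. The fixed denominator does count a subject with gaps and no recorded reaction as having no onset; the completeness tables already planned in section 13.1.1 let a reader judge how much that matters.
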